5.0 METHODOLOGY

5.1 Entry Criteria

Subject Inclusion Criteria

In order to be eligible for participation in this trial, the subject must:

1. Be willing and able to provide written informed consent/assent for the trial.
2. Be ≥ 18 years of age on day of signing informed consent.
3. Have metastatic melanoma or NSCLC, or locally advanced NSCLC not suitable for curative-intent local therapy.
4. For melanoma patients and NSCLC patients treated with prior anti-PD-1 therapy, patients must have received prior PD-1 therapy and have progressed (irPD) by irRC.
5. Have 2 or more measurable sites of disease as defined by either RECIST 1.1, or cutaneous lesions at least 1 cm in greatest dimension
6. Have at least one site of disease that is considered potentially suitable for treatment with SBRT
7. Have provided tissue from an archival or newly obtained tissue sample of a tumor lesion, sufficient for analysis of PD-L1 and other biomarkers. Patients who have had PD-L1 analysis previously performed at Merck can substitute earlier analysis results and are not required to submit additional tissue for PD-L1 testing. Expression of PD-L1 is NOT required for study entry.
8. Have a performance status of 0, 1 or 2 on the ECOG Performance Scale.
9. Demonstrate adequate organ function as defined in Table 1, all screening labs should be performed within 28 days of protocol treatment.

Table 1 Adequate Organ Function Laboratory Values

System	Laboratory Value
Hematological	
Absolute neutrophil count (ANC)	$\geq 1,500$ /mcL
Platelets	$\geq 100,000$ / mcL
Hemoglobin	≥ 9 g/dL
Renal	

Serum creatinine OR Measured or calculated ^a creatinine clearance (GFR can also be used in place of creatinine or CrCl)	$\leq 1.5 \times$ upper limit of normal (ULN) OR $\geq 60 \text{ mL/min}$ for subject with creatinine levels $> 1.5 \times$ institutional ULN
Hepatic	
Serum total bilirubin	$\leq 1.5 \times$ ULN OR
Direct bilirubin	Direct bilirubin \leq ULN for subjects with total bilirubin levels $> 1.5 \times$ ULN
AST (SGOT) and ALT (SGPT)	$\leq 2.5 \times$ ULN OR $\leq 5 \times$ ULN for subjects with liver metastases

^aCreatinine clearance should be calculated per institutional standard.

10. Female subject of childbearing potential should have a negative urine or serum pregnancy within 72 hours prior to receiving the first dose of study medication. If the urine test is positive or cannot be confirmed as negative, a serum pregnancy test will be required.
11. Female subjects of childbearing potential must be willing to use an adequate method of contraception as outlined in section 5.6 – Contraception, for the course of the study through 120 days after the last dose of study medication.

Note: Abstinence is acceptable if this is the usual lifestyle and preferred contraception for the subject.

12. Male subjects of childbearing potential must agree to use an adequate method of contraception as outlined in section 5.6 – Contraception, starting with the first dose of study therapy through 120 days after the last dose of study therapy.

Note: Abstinence is acceptable if this is the usual lifestyle and preferred contraception for the subject.

Subject Exclusion Criteria

The subject must be excluded from participating in the trial if the subject:

1. Has had radiation therapy within 2 weeks of the first protocol treatment.
2. Is currently participating in or has participated in a study of an investigational agent or using an investigational device within 2 weeks of the first protocol treatment.
3. Has a diagnosis of immunodeficiency or is receiving systemic steroid therapy or any other form of immunosuppressive therapy within 2 weeks of the first protocol treatment. The use of low-dose steroids for management of chronic conditions is allowed.
4. Non-small cell lung cancer patients enrolling to MK-3475 as first protocol therapy (no prior anti-PD-1 therapy): Has had a prior monoclonal antibody within 4 weeks prior to first protocol treatment or who has not recovered (i.e., \leq Grade 1 or at baseline) from adverse events due to agents administered more than 4 weeks earlier.
5. Has had prior chemotherapy, targeted small molecule therapy, or radiation therapy within 2 weeks of the first protocol treatment or who has not recovered (i.e., \leq Grade 1 or at baseline) from adverse events due to a previously administered agent.

- Note: Subjects with \leq Grade 2 neuropathy are an exception to this criterion and may qualify for the study.
- Note: Patients who have had prior treatments with Tyrosine Kinase Inhibitors (e.g. Tarceva) require only a 72-hour washout period prior to starting protocol treatment.

6. Has a known additional malignancy that is progressing or requires active treatment. Exceptions include basal cell carcinoma of the skin, squamous cell carcinoma of the skin, or *in situ* cervical cancer that has undergone potentially curative therapy.
7. Has known active and untreated brain (CNS) metastases and/or carcinomatous meningitis. Subjects with previously treated brain metastases may participate.
8. Has an active autoimmune disease requiring systemic treatment within the past 3 months or a documented history of clinically severe autoimmune disease, or a syndrome that requires systemic steroids or immunosuppressive agents. Subjects with vitiligo or resolved childhood asthma/atopy would be an example of an exception to this rule. Subjects that require intermittent use of bronchodilators or local steroid injections would not be excluded from the study. Those with a history of hypothyroidism who are now stable on hormone replacement will not be excluded. Those with Sjorgen's syndrome will not be excluded from the study.
9. Has a history of (non-infectious) pneumonitis that required steroids, current pneumonitis or evidence of interstitial lung disease.
10. Has an active infection requiring systemic therapy.
11. Has known psychiatric or substance abuse disorders that would interfere with cooperation with the requirements of the trial.
12. Is pregnant or breastfeeding, or expecting to conceive or father children within the projected duration of the trial, starting with the screening visit through 120 days after the last dose of trial treatment.
13. Has a known history of Human Immunodeficiency Virus (HIV) (HIV 1/2 antibodies).
14. Has known active Hepatitis B (e.g., HBsAg reactive) or Hepatitis C (e.g., HCV RNA [qualitative] is detected).
15. Has received a live vaccine within 30 days prior to the first protocol treatment.

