5.2.1 Study Design

This is a two-part study, including both phase 1b and 2a portions.

The **phase 1b** is an SBRT dose escalation study, in which patients with both NSCLC and melanoma will be enrolled. NSCLC patients will be enrolled and treated with MK-3475 until they have progression of disease (irPD). Patients who have progression within 12 months of study entry will be evaluated for SBRT and re-initiation of MK-3475. Patients who do not have progression of disease within that timeframe may continue to receive MK-3475 for up to 18 months per protocol. These patients will not be evaluable for the study endpoints, although their response rates and overall survival will be reported.

Melanoma and selected NSCLC patients will be enrolled after having progression of disease on prior PD-1 therapy (irPD). They will be immediately treated with SBRT, followed by re-initiation of MK-3475.

After progression of disease on an initial course of anti-PD-1 therapy (either prior to enrollment, or during trial therapy), a target for SBRT will be selected and patients will be assigned to one of two arms on the basis of the anatomic location of the target (Arm A: lung, Arm B: non-lung). The SBRT target will be chosen and ideally SBRT will be delivered as quickly as feasible after the last infusion of MK-3475. NSCLC patients who do not have a suitable SBRT target (as defined in section 5.2.3) on the imaging study that shows progression of disease may undergo interval re-imaging without further therapy, but if no suitable target has been identified for SBRT within 12 weeks of the last infusion of MK-3475, that patient will be removed from treatment and moved to survival follow up.

Patients may continue to receive MK-3475 post disease progression while radiation therapy with SBRT is scheduled. Patients who require continuing corticosteroid treatment, or who have adverse events (grade 3 or greater non-hematologic, or grade 2 pneumonitis) due to MK-3475 that do not resolve within 12 weeks of AE start date will not receive SBRT and will also be removed from study. Patients who develop grade 3 pneumonitis will be removed from the study, regardless of whether it resolves. SBRT will be delivered in dose cohorts as described below in section 5.3.

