The first fraction of SBRT should be delivered as soon as feasible after progression of disease. For the following events, SBRT should be delayed until they resolve (for toxicities, to grade 0 or 1), up to 12 weeks after the last infusion of MK-3475. If the listed events do not resolve within 12 weeks of the last infusion of MK-3475, the patient will be removed from the study and replaced.

1. Grade 2 or greater pneumonitis
2. Corticosteroid use within 2 weeks of SBRT, except in individual cases allowed by the Principal Investigator
3. Grade 3 or greater non-hematologic toxicity related to study therapy

Patients who develop grade 3 or greater pneumonitis during the pre-SBRT MK-3475 will be taken off of the study, and will not be eligible for SBRT, or re-initiation of MK-3475.

Patients will be treated on non-consecutive days whenever possible, with all fractions to be scheduled within 15 calendar days from first to last. Localization of the tumor target before each fraction is required, by either cone-beam CT scan, kilovoltage on -board imaging, or an internal fiducial.

SBRT Dose Modification and Supportive Care

SBRT will be discontinued if any grade 3 or greater adverse event occurs during radiation treatment that is probably or definitely attributable to radiation. This will be counted as a DLT if it occurs during the phase Ib portion of the study. These patients will be allowed to continue with trial therapy (the second course of MK-3475, but not the remainder of their SBRT) if the toxicity resolves to grade 0 or 1 with supportive measures within 12 weeks of AE start date.

SBRT will also be discontinued if the completion of all fractions is prolonged beyond 30 days for reasons unrelated to toxicity (i.e., intercurrent illness, or patient refusal). This will not be counted as a DLT, and these patients will be allowed to continue with trial therapy (the second course of MK-3475, but not the remainder of their SBRT) as long as the investigator believes that they will be compliant with the remainder of the trial therapy. In the phase Ib portion of the study, these patients will not be counted towards the minimum number of patient treated at that dose level as long as they have not experienced a DLT before treatment is abort, but instead will be replaced. If they have experienced a DLT during that period, then they will be counted toward that dose cohort.

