No other SBRT dose modification for individual patients is permitted during the phase Ib portion of the study. During the phase 2a portion, at the discretion of the treating radiation oncologist and with the agreement of the principal investigator, the prescription dose for SBRT may be reduced in an effort to reduce the risk of toxicity. In this case, one of the 3 dose levels specified in the dose escalation section 5.3 will be used.

Adverse events that occur during or after SBRT should be managed per section 5.5, or with best supportive care.

53 SBRT Dose-Escalation or De-Escalation

In the Phase 1b (SBRT dose escalation/de-escalation) portion, patients will be allocated to Arm A (Lung) or Arm B (non-Lung) based on the anatomic site of the target chosen for SBRT. Dose escalation or de-escalation will be done separately for each arm, and the MTD determined separately for each arm. Once an MTD has been determined for lung and non-lung targets, future patients with those SBRT targets will be allocated to the Phase IIa portion of the trial.

In the Phase 2a (expansion) portion, patients will be treated at the SBRT MTD for lung or non-lung lesions, as appropriate.

Dose-Escalation or De-Escalation

In the Phase Ib portion of the trial, the SBRT dose will be escalated or de-escalated in successive cohorts. The starting dose will be 3000 cGy in 5 fractions. A single de-escalation cohort (1000 cGy in a single fraction), and a single escalation cohort (3000 cGy in 3 fractions) will be allowed.

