5.7 Subject Withdrawal/Discontinuation Criteria

Subjects may withdraw consent at any time for any reason or be dropped from the trial at the discretion of the investigator should any untoward effect occur. In addition, a subject may be withdrawn by the investigator if enrollment into the trial is inappropriate, the trial plan is violated, or for administrative and/or other safety reasons. Specific details regarding discontinuation or withdrawal are provided in Section 7.

A subject must be discontinued from treatment, or removed from the study for any of the following reasons:

- The subject or legal representative (such as a parent or legal guardian) withdraws consent.
- Progression of disease during the second course of MK-3475 (as defined in section 5.2.1)
- Unacceptable adverse experiences as described in Section 5.2
- Intercurrent illness that prevents further administration of treatment
- Investigator's decision to withdraw the subject
- The subject has a confirmed positive serum pregnancy test

- Noncompliance with trial treatment or procedure requirements
- The subject is lost to follow-up
- Completed 12 months of treatment with post-SBRT MK-3475
Note: 12 months of study medication is calculated from the date of first dose of the second course. Subjects who stop MK-3475 after 12 months will be eligible for up to one year of additional study treatment if they progress after stopping study treatment
- Administrative reasons

The End of Treatment and Follow-up visit procedures are listed in Sections 6 and 7. After the end of treatment, each subject will be followed for 30 days for adverse event monitoring (serious adverse events will be collected for 90 days after the end of treatment as described in Section 8). Subjects who discontinue treatment will be followed for survival until death, withdrawal of consent, or the end of the study, whichever occurs first. Survival follow up may be a phone call only.

58 Subject Replacement Strategy

In both phases of the study, patients will be replaced if

1. They do not complete at least one fraction of SBRT.
2. They do not complete their entire course of SBRT as prescribed due to reasons other than toxicity (e.g., patient refusal, or intercurrent illness).

59 Clinical Criteria for Early Trial Termination

Early trial termination will be the result of the criteria specified below:

1. Quality or quantity of data recording is inaccurate or incomplete
2. Poor adherence to protocol and regulatory requirements

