Pregnancy Test – Urine or Serum β-HCG	X ⁷								
Archival or Fresh Tumor Collection ⁴	X ²								
CBC with Differential	X		X	X	X	X			
CMP, LDH	X		X	X	X	X			
TSH & Free T4 ¹⁰	X			X		X			
Selection of SBRT target									
Blood for correlative studies	X ⁸	X ⁸	X ⁸	X ⁵	X ⁵	X ⁵	X		
Survival Follow-up									X
Administer study drug, MK-3475 ⁶			X ⁷	X	X	X			

¹ During week 3 every 2 cycles (during the last week of cycles 2 and 4), and then every 4 cycles (at the end of cycles 8, 12, etc.)

² Includes PD-L1 testing

³ Study visit the last day of SBRT

⁴ When feasible, if a biopsy is done for clinical purposes as per standard of care at any point during a subject's participation on trial, tissue may be collected at the time of the biopsy

⁵ Blood for correlative studies will be drawn at cycles 2 through 4 for both pre- and post-SBRT, then every even-numbered cycle thereafter (e.g. 6, 8, 10, etc.). If MK-3475 is held for any reason when blood for correlative samples is to be drawn, the blood may be drawn at the discretion of the Principal Investigator. When MK-3475 is resumed, blood for correlative samples will be taken as per the calendar above.

⁶ Will be started following SBRT as soon as possible every 3 weeks on Day 1 of each cycle (+/- 7 days) until progression. Drug may be administered for up to 12 months from the first dose of the second course. Subjects who stop drug after 12 months will be eligible for up to 1 year of additional treatment if they progress after study drug is stopped.

⁷ Pregnancy test within 72 hours of first dose of study medication for WOCBP

⁸ Correlative lab draw can be taken either post-SBRT and/or prior to cycle 1 dose of MK-3475 following SBRT. Both are not required, but can be collected.

⁹Required 30 days (+/- 7 days) from the End of Treatment visit, unless there were no toxicities > Grade 1 probably, or definitely related to protocol treatment at the End of Treatment visit. In this case, the End of Treatment visit will suffice as the safety follow up visit.

¹⁰ After the screening period, TSH and Free T4 to be done every other cycle starting with week 2

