7.2 Screening Period

Prior to initiation of study therapy, the patient will require a screening visit(s). Scans, evaluations, and laboratory studies should be done as close to the initiation of therapy as feasible, and no more than 28 days prior. The following should be addressed during the screening period:

1. Informed Consent
2. Medical History
3. Complete physical examination, vital signs, and measurement of height and weight (pre-recorded height may be used from medical record)
4. Review of prior and concomitant medications
5. CT scan of chest, abdomen and pelvis (a PET/CT scan will be deemed sufficient)
6. Performance status evaluation
7. Determination of baseline adverse event status
8. Pregnancy test for women of childbearing potential, and counseling that sexually active women of childbearing potential must use an effective form of birth control during the entire study period
9. Determination of sufficient tumor specimen for evaluation of PD-L1 status
10. Laboratory studies: CBC with differential, serum chemistries, liver function tests, LDH, TSH and Free T4
11. Submission of blood for correlative studies (see footnote 5 above in the non-small cell lung cancer calendar and footnote 9 above in the melanoma calendar)

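### For patients who start with SBRT, the 72-hour pregnancy-test limit is tied to the first MK-3475 dose, so the test before irradiation may be up to 28 days old

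*Combined protocol and SAP*

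**What the plan says.** - **Eligibility.** Section 5.1, inclusion criterion 10: a woman of childbearing potential "should have a negative urine or serum pregnancy within 72 hours prior to receiving the first dose of study medication".
- **Order of treatment.** Section 5.2.1, on melanoma and selected NSCLC patients who progressed on earlier PD-1 therapy: "They will be immediately treated with SBRT, followed by re-initiation of MK-3475". Their calendar in section 6.0 places the SBRT column between screening and MK-3475 cycle 1.
- **Calendar.** The pregnancy row for these patients has one mark, in the screening column (days -28 to -1). That mark carries footnote 7: "Pregnancy test within 72 hours of first dose of study medication for WOCBP". The same footnote is attached to the cycle 1 MK-3475 cell. Neither the SBRT column nor cycle 1 has a mark in the pregnancy row.
- **Screening.** Section 7.2 lists the pregnancy test among the screening procedures under the general rule: "Scans, evaluations, and laboratory studies should be done as close to the initiation of therapy as feasible, and no more than 28 days prior".
- **SBRT schedule.** Section 5.3: "The starting dose will be 3000 cGy in 5 fractions". Section 5.2.3: "Patients will be treated on non-consecutive days whenever possible, with all fractions to be scheduled within 15 calendar days from first to last".

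**The concern.** Pregnancy is an exclusion (criterion 12), and the protocol's own standard for a recent negative test is 72 hours. That standard works when MK-3475 is the first treatment, as it is for NSCLC patients with no earlier anti-PD-1 therapy. Their calendar carries the identical footnote (number 11). On the SBRT-first route the wording is unchanged but the order of treatment is reversed, so the limit falls on the second treatment.

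Two things follow. A woman can begin irradiation on a negative test that is up to 28 days old without breaching any stated limit. And sites must work out for themselves whether footnote 7 calls for a second test after SBRT, because the only mark in the pregnancy row is at screening.

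**Working it through.** **1. What *study medication* refers to.** The term is not formally defined, so its meaning has to be read from usage.
- Section 5.7, under the limit on post-SBRT MK-3475, states: "12 months of study medication is calculated from the date of first dose of the second course". That is a count of drug dosing.
- Note c to Table 4, the MK-3475 dose-modification table, uses *study medication* and *study drug* interchangeably.
- Footnote 7 is attached to the cycle 1 MK-3475 cell and not to the SBRT column.

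All three point to MK-3475. The washout exclusions use a different anchor, as in exclusion 1: "Has had radiation therapy within 2 weeks of the first protocol treatment". Exclusions 1 to 5 and 15 are all counted from the first protocol treatment, which is SBRT for these patients.

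**2. Maximum test age at fraction 1.** The screening column runs from day -28 to day -1, and section 7.2 sets the same 28-day ceiling. The test is therefore 1 to 28 days old at fraction 1. Under a 72-hour limit counted from fraction 1, the maximum would be 3 days.

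**3. Can one test meet both the screening column and footnote 7?** Let fraction 1 be day 1 and the last fraction be day L. Assume MK-3475 is given on day L, the earliest case; each day of delay moves the window one day later. Then:
- the 72-hour window opens on day L - 3;
- the age of a screening test at the first MK-3475 dose runs from (L - 1) + 1 = L days to (L - 1) + 28 = L + 27 days.

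Dose per fraction is 30/5 = 6 Gy, 30/3 = 10 Gy or 10/1 = 10 Gy.

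| Schedule | L | Window opens | Target dose already given | Age of screening test at MK-3475 |
|---|---|---|---|---|
| 5 fractions, consecutive days | 5 | day 2 | 1 × 6 = 6 Gy | 5–32 days |
| 5 fractions, alternate days | 9 | day 6 | 3 × 6 = 18 Gy (days 1, 3, 5) | 9–36 days |
| 5 fractions, last on day 15 | 15 | day 12 | depends on spacing | 15–42 days |
| 3 fractions, alternate days | 5 | day 2 | 1 × 10 = 10 Gy | 5–32 days |
| 3 fractions, consecutive days | 3 | day 0 | none | 3–30 days |
| 1 fraction | 1 | day -2 | none | 1–28 days |

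Day 0 here is the day before fraction 1. In every 5-fraction schedule, and with 3 alternate-day fractions, the window opens after fraction 1. The youngest possible screening test is then 5 days old at MK-3475, against a limit of 3. One test can serve both purposes only with a single fraction, or with three consecutive daily fractions, and only if MK-3475 follows promptly.

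**The case against.** The strongest reply is that the anchor may be deliberate. Section 5.6 names only MK-3475 as a fetal risk, Table 2 labels SBRT as standard treatment, and no text sets a 72-hour test before radiation on either route. On this view the screening mark provides the test before SBRT, footnote 7 provides one before the drug, and the missing cycle 1 mark is only a layout fault. Other protections apply: exclusion 12 bars pregnancy and planned conception from the screening visit, inclusion 11 requires contraception during the study, and section 7.2 requires counselling. Section 7.2 also asks for screening work to be done as near to the start of therapy as is practicable, so a 28-day-old urine test would strain its intent.

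Part of this stands. The 28 days are an outer bound, not typical practice. The doses in the table are tumour-target doses that show where the window falls; they are not fetal exposure. The pre-drug test is indeed already required by inclusion 10. The meaning of *study medication* is an inference, though a consistent one.

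It does not close the gap. A request for feasible proximity is not a limit, and neither the exclusion nor the contraception rules date a test. If *study medication* were instead meant to include SBRT, footnote 7 on the MK-3475 cell would be misplaced and the wording would still need correction. NSCLC patients without prior anti-PD-1 therapy may also reach SBRT long after their screening test; that is a separate gap and is not part of this point.

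**Conclusion.** The concern holds for melanoma patients and NSCLC patients with prior anti-PD-1 therapy. The only firm limit on the age of the pregnancy test at first irradiation is 28 days, whereas the protocol's own 72-hour standard would make it 3 days. At the starting dose, the single test shown in the calendar cannot satisfy its own footnote, even on the most favourable schedule.

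This rests on reading *study medication* as MK-3475 and on MK-3475 being given no earlier than the day of the last fraction. It is a patient-safety correction that should be made, and it has no bearing on endpoints, sample size or dose escalation. No estimate of how often it would matter is possible, because the documents do not give the number of women of childbearing potential.

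**What to change.** 1. In inclusion criterion 10 and footnote 7, require a negative test within 72 hours before the first protocol treatment, whether that is SBRT or MK-3475. The existing screening test is then timed to fraction 1 on the SBRT-first route.
2. For SBRT-first patients, keep the test within 72 hours before the first MK-3475 dose and mark it in the cycle 1 column of their calendar.
3. In section 5.6, start the contraception requirement at the first protocol treatment instead of at study drug initiation. Inclusion 11, exclusion 12 and section 7.2 already cover the whole study, so this only aligns the wording.

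The cost is a wording amendment and at most one repeat urine or serum test per woman of childbearing potential on this route. No repeat is needed when one test falls within 72 hours of both treatments.
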